#### 7.4.1.2 *Effect of food:*

In 2 studies in healthy subjects (the first study using the clinical trial formulation and the second using the market-image formulation), concomitant administration of a high fat meal resulted in a minimal change in the bioavailability of duvelisib. On average,  $C_{\max}$  decreased by 10% in the first study and 37% in the second; median  $t_{\max}$  was slightly delayed from 1 hour (fasted) to 3 hours (fed) in the first study and 4 hours (fed) in the second. However, overall exposure, as assessed by  $AUC_{(0-\text{last})}$  and  $AUC_{(0-\text{inf})}$ , increased by 8%-9% in the first study and decreased 2%-6% in the second study. These data indicate that duvelisib may be administered without regard to meals. Please refer to individual study protocols for specific instructions related to fasting or fed status in relation to collection of PK or other clinical samples.

#### 7.4.1.3 *Concomitant use with other agents:*

CYP3A4 has been identified as the primary contributor to the metabolism of duvelisib. In Study IPI-145-01, exposure to duvelisib increased approximately 4-fold in the presence of the strong CYP3A inhibitor ketoconazole, and decreased approximately 80% in the presence of rifampin, a CYP3A inducer. For these reasons, the concomitant use of drugs or foods that are strong inhibitors or inducers of CYP3A is not allowed during treatment with duvelisib.

In vitro studies in human liver microsomes demonstrated that duvelisib and its primary metabolite IPI-656 are reversible inhibitors of CYP3A4 and CYP2C8 and mechanism-based inhibitors of CYP3A4.

Coadministration of duvelisib (25 mg BID for 5 days) with MDZ (a sensitive CYP3A substrate) resulted in an approximate 4-fold increase in MDZ systemic exposure (AUC) compared to administration of MDZ alone. Systemic exposure to other medications that are substrates for CYP3A4 may be increased in subjects receiving duvelisib. Caution should be used if duvelisib is administered concomitantly with drugs that are substrates for CYP3A, particularly those with a narrow therapeutic range. Drugs that are substrates for CYP3A should be used only if medically necessary and therapeutic alternatives are not available.

Based on plasma concentrations following administration of 25 mg BID, duvelisib is not expected to increase the exposure of medications metabolized via CYP2C8; however, a clinical study with a CYP2C8 substrate has not been conducted. Medications that are metabolized via CYP2C8 may be used as medically indicated but with caution.

## 7.5 Expedited Adverse Event Reporting

7.5.1 Investigators **must** report to the Overall PI any serious adverse event (SAE) that occurs after signing the consent form, during treatment, or within 30 days of the last dose of treatment on the local institutional SAE form.

CONFIDENTIAL

This document is confidential. Do not disclose or use except as authorized.

If the participant goes on to another SLL/CLL or RS directed therapy before the 30-day period, the reporting period ends when they begin new treatment.

### 7.5.2 DF/HCC Expedited Reporting Guidelines

Investigative sites within DF/HCC will report SAEs directly to the DFCI Office for Human Research Studies (OHRS) per the DFCI IRB reporting policy.

External (Non-DF/HCC) sites will send their report to the lead site project manager and Overall PI for review and submission to the appropriate entities according to DFCI IRB policies and procedures in reporting adverse events.

The following adverse events must be reported to the DFCI IRB according to the expedited reporting guidelines:

- **CTCAE Grade 2 and Grade 3 Events** – that are *Unexpected* and there is a *Reasonable Possibility* that the *Adverse Event* is related to the study Intervention.
- **CTCAE Grade 4 Events** – Report all events that are *Unexpected*. Events that are *Expected* and listed within the protocol and/or current consent form do not need to be reported to the DFCI IRB.
  - Please note, an event that presents at a higher severity than what is currently listed within the protocol and/or current consent as expected would be considered unexpected and reportable.
- **ALL CTCAE Grade 5 Events.**

**When assessing expectedness, investigators should consult the investigator’s brochure, package insert, and the most current version of the informed consent form.**

### 7.5.3 External Site Adverse Event Reporting Guidelines

In addition to following the SAE reporting requirements for DFCI and Secura Bio, other participating investigative sites will report SAEs to their respective IRB per the local IRB’s policies and procedures.

CONFIDENTIAL

This document is confidential. Do not disclose or use except as authorized.

For Multi-Center Trials where a DF/HCC investigator is serving as the Sponsor, each participating institution must abide by the reporting requirements set by the DF/HCC. Criteria for reporting to DFCI listed in section 7.5.3. The lead site will report external site SAEs to the DFCI IRB on the external site's behalf after review and approval by the overall PI.

This applies to any medical event equivalent to an unexpected grade 2 or 3 with a possible, probable or definite attribution, unexpected 4 toxicities and grade 5 (death) regardless of study phase or attribution.

## 7.6 Reporting to the Food and Drug Administration (FDA)

The Overall PI, as study sponsor, will be responsible for all communications with the FDA. The Overall PI will report to the FDA, regardless of the site of occurrence, any serious adverse event that meets the FDA's criteria for expedited reporting following the reporting requirements and timelines set by the FDA.

## 7.7 Routine Adverse Event Reporting

All Adverse Events **must** be reported in routine study data submissions to the Overall PI on the toxicity case report forms. **AEs reported through expedited processes (e.g., reported to the IRB, FDA, etc.) must also be reported in routine study data submissions.**

## 7.8 Expedited Reporting to Hospital Risk Management

Participating investigators will report to their local Risk Management office any participant safety reports or sentinel events that require reporting according to institutional policy.

# 8. PHARMACEUTICAL INFORMATION

## 8.1 Duvelisib

### 8.1.1 Description

Duvelisib is a potent oral inhibitor of the delta- and gamma-isoforms of PI3K. Duvelisib is rapidly absorbed following oral administration, with maximal concentrations occurring approximately 0.5 to 2 hours after dosing. Exposure (AUC) increased proportionally with doses through 75 mg PO BID. The half-life was 7 hours, regardless of dose. The mean pre-dose steady state plasma concentration following 25 mg BID was 425 ng/mL, indicating suppression of PI3K-delta (IC90=361 ng/mL) and PI3K-gamma (IC50=429 ng/mL) throughout the dosing interval. Pharmacodynamic studies confirmed rapid, profound and sustained inhibition of AKT phosphorylation by duvelisib in CLL cells, as well as decreased levels of chemokines such as CCL3 and CCL4, which are important for

CONFIDENTIAL

This document is confidential. Do not disclose or use except as authorized.

lymphocyte trafficking. The MTD of duvelisib as monotherapy for CLL has been determined to be 75 mg BID, but the recommended phase 2 dose is 25 mg bid, which was chosen as the optimal balance of safety and efficacy.

#### 8.1.2 **Form:**

Duvelisib is supplied as 25 mg (size 2 white hard) gelatin capsules for oral delivery. Patients in this study will receive 25 mg BID as initial dosing.

#### 8.1.3 **Storage and Stability**

Duvelisib must be stored at room temperature (15 to 30°C) and protected from light.

If a temperature excursion is experienced at any investigational site/institution beyond the stated storage parameters, the site must report the excursion and associated details to the lead site project manager as soon as the excursion is identified.

#### 8.1.4 **Compatibility**

NA

#### 8.1.5 **Handling**

Qualified personnel, familiar with procedures that minimize undue exposure to themselves and the environment, should undertake the preparation, handling, and safe disposal of the chemotherapeutic agent in a self-contained and protective environment.

Caution is required when handling duvelisib. Pharmacists should follow standard procedure for the handling of investigational drugs, including avoidance of eye or skin contact with the drug product. If there is exposure to the drug product, provide treatment as necessary for physical exposure (skin washing) or inhalation (move to fresh air) and seek medical advice as necessary.

When duvelisib capsules are distributed for self-administration, they should only be handled by the study subject. After handling capsules, the subject should wash their hands thoroughly. If someone who is not enrolled in a clinical trial involving duvelisib swallows a capsule or inhales drug powder from a broken capsule of duvelisib, they should contact the relevant Principal Investigator to determine whether safety monitoring is necessary. Capsules should always be stored in the container provided to the study subject.

#### 8.1.6 **Availability**

Duvelisib is an investigational agent and will be supplied by Secura Bio, Inc.

CONFIDENTIAL

This document is confidential. Do not disclose or use except as authorized.

### 8.1.7 Preparation

Duvelisib will be supplied to the clinical trial site as open-label medication. Capsules are packaged in thermoform blister cards with peel and push child-resistant lidding. The label attached to each blister card will include, at a minimum, a statement limiting its use for investigational study only.

### 8.1.8 Administration

Duvelisib is administered orally as a capsule formulation as a fixed dose in mg and should be administered using the minimal number of capsules necessary.

### 8.1.9 Ordering

The DF/HCC pharmacy will order duvelisib from an investigational stock directly from Secura Bio, Inc. who will be providing the study drug.

External (Non-DF/HCC) investigative sites will be provided with a study specific drug order form by the lead site project manager once all necessary documents are collected, and the site is otherwise approved to enroll participants on the study.

The drug will be provided at no cost to the participant.

If necessary, the drug may be shipped to the participant's home from the investigative site pharmacy without specific approval from the overall PI. The shipment must be sent via traceable carrier, and confirmation of receipt must be filed in the participant's study file

### 8.1.10 Accountability

The investigator, or a responsible party designated by the investigator, will maintain a careful record of the inventory and disposition of duvelisib using a drug accountability form that is compliant with local and federal guidelines.

Additionally, a designated study team member will complete drug accountability/reconciliation based on the participant actual drug return versus the anticipated drug return and document the findings according to local and federal regulations and guidance.

### 8.1.11 Destruction and Return

After full drug accountability and reconciliation, all unused duvelisib will be destroyed according to local site procedures and policies. Destruction will be documented in the Drug Accountability Record Form. If any study drug is lost or damaged, the disposition

CONFIDENTIAL

This document is confidential. Do not disclose or use except as authorized.

of the study drug should be documented. Patients should be instructed to bring all unused duvelisib to each study visit. The study site should count all capsules that the patient returns, and should take account for missed doses, doses reduced due to missing or lost capsules, etc., before dispensing new study drug to the patient. Any patient who does not take the prescribed dose should be requested to return the remaining drug to the clinical trial site for accountability.

## 8.2 Venetoclax

CONFIDENTIAL

This document is confidential. Do not disclose or use except as authorized.

### 8.2.1 Description:

Venetoclax (ABT-199/GDC-0199) is a novel, orally bioavailable, small-molecule BCL-2 family inhibitor in the biarylacylsulfonamide chemical class. Venetoclax binds with high affinity ( $K_i < 0.010$  nM) to antiapoptotic protein BCL-2 and with lower affinity to other antiapoptotic Bcl-2 family proteins, like BCL-XL and BCL-w ( $> 4,800$ -fold and  $> 24,500$ -fold lower affinity than to Bcl-2, respectively).

In vitro studies have shown that venetoclax was metabolized primarily by CYP3A4/5. Interaction of venetoclax with co-administered CYP3A inhibitors or inducers may cause an increase or decrease in the exposure of venetoclax. In vivo, venetoclax was also demonstrated to be metabolized by CYP3A4/5. Venetoclax is also substrate for P-glycoprotein (P-gp) and breast cancer resistance protein (BCRP) transporters. Renal contribution to the elimination of venetoclax is negligible, with  $< 0.1\%$  of the dose being recovered in urine. Based on in vitro results, venetoclax was a P-gp, BCRP, and OATP1B1 inhibitor. It was not a potent in vitro inhibitor of CYP3A4, CYP1A2, CYP2B6, or CYP2D6 ( $IC_{50} > 30$   $\mu$ M); and it did not induce CYP3A4 or CYP1A2 at concentrations up to 10  $\mu$ M. Venetoclax is also not predicted to cause inhibition of CYP2C19, CYP2C8, CYP2C9, and UGT1A1 at clinically relevant concentrations. It is not an inhibitor of UGT1A4, UGT1A6, UGT1A9 and UGT2B7. Following co-administration of a single dose of venetoclax with warfarin, R- and S-warfarin  $C_{max}$  and  $AUC_{\infty}$  increased by approximately 18% to 28%. Relatively low variability was observed in warfarin PK.

The venetoclax formulation currently used in clinical studies is a tablet formulation with strengths of 10, 50, and 100 mg. The tablet formulation was orally administered after a low-fat meal. Food increased the bioavailability of venetoclax by 3- to 4-fold. Preliminary pharmacokinetic results indicated that the absorption of venetoclax after the oral dosing was relatively slow. Venetoclax plasma concentrations peaked at approximately 5 to 8 hours after dosing. Mean harmonic terminal phase half-life from 17 to 41 hours and the mean oral clearance was approximately 13 L/hr after a single dose. Preliminary data did not suggest apparent pharmacokinetics differences among subjects with CLL/SLL, NHL, Multiple Myeloma (MM), Acute Myeloid Leukemia (AML), or SLE. The combined data from subjects with CLL/SLL and NHL suggested that venetoclax exposure was approximately dose proportional across the 150 to 800 mg dose levels at steady state. Additional information about venetoclax is available in the package insert.

### 8.2.2 Form:

Venetoclax tablets are film coated and are available in strengths of 10 mg, 50 mg, or 100 mg. Venetoclax will be packaged in high density polyethylene (HDPE) plastic bottles. Each bottle will be labeled per local regulatory requirements. Labels must remain affixed to the bottle.

CONFIDENTIAL

This document is confidential. Do not disclose or use except as authorized.

**8.2.3 Storage and Compatibility:**

Venetoclax must be stored at 15° to 25°C (59° to 77°F) per package insert

**Compatibility:**

N/A

**8.2.4 Handling:**

Qualified personnel, familiar with procedures that minimize undue exposure to themselves and the environment, should undertake the preparation, handling, and safe disposal of the agent in a self-contained and protective environment.

**8.2.5 Availability:**

Patients are required to have access to a commercial supply of venetoclax.

**8.2.6 Preparation**

N/A

**8.2.7 Administration:**

Oral. Patients should take venetoclax tablets with a meal and water at approximately the same time each day, preferably about 30 minutes after breakfast. Venetoclax tablets should be swallowed whole and not chewed, crushed, or broken prior to swallowing.

**8.2.8 Ordering**

Supplies of venetoclax will be procured through the participant's insurance via commercial supply through an appropriate specialty pharmacy.

**8.2.9 Accountability:**

Venetoclax is commercially sourced therefore, no drug accountability records are required.

**8.2.10 Destruction and Return:**

Destruction of used and unused study drug may be performed as per institutional policy.

CONFIDENTIAL

This document is confidential. Do not disclose or use except as authorized.

## 9. BIOMARKER, CORRELATIVE, AND SPECIAL STUDIES

While the goal of the correlative studies is to provide supportive data for the clinical study, there may be circumstances when a decision is made to stop a collection, not perform, or discontinue an analysis due to either practical reasons (e.g., inadequate sample number, issues related to the quality of the sample or issues related to the assay that preclude analysis, impossibility to perform correlative analyses, etc). Therefore, depending on the results obtained during the study, sample collection/analysis may be omitted at the discretion of the PI.

Samples collected on this study may be used for future research studies, including genetic research. Samples may also become part of a biobank, a biorepository that accepts, processes, stores and distributes biospecimens and associated data for use in research and clinical care.

### 9.1 BH3 Profiling:

BH3 profiling is a functional assay that detects the proximity of cells to the threshold of apoptosis (i.e. priming) through interrogation of BCL-2 family members. To perform a BH3 profile, we add individual peptides, which bind to the BH3-only region of anti-apoptotic proteins, to gently permeabilized malignant cells. We then use Fluorescence-activated cell sorting (FACS) to measure the amount of mitochondrial depolarization induced by each peptide, as measured by cytochrome c release. Previous trials at our institution have suggested that this technique may be useful as an effective predictor of response in CLL.

We hypothesize that patients whose cells undergo significant depolarization to the BIM BH3 peptide (primed) will have superior clinical response to duvelisib plus venetoclax as compared to patients whose cells undergo minimal BIM BH3 depolarization (unprimed). These assessments will be made on circulating CLL cells from the peripheral blood drawn from patients at baseline and after three and six months of combination therapy.

If we have bone marrow aspirates available, we will also perform BH3 profiling to see whether the level of priming in CLL cells from these tissues is a better predictor of response than peripheral blood CLL cells.

After 1 week of duvelisib monotherapy on cycle 1 day 8 (prior to receiving venetoclax), we will obtain another peripheral blood sample. We will compare the BH3 profile of this steady-state sample to a baseline sample, which will allow us to assess the short term change in apoptotic priming induced by in vivo duvelisib as a single agent.

Lastly, peripheral blood will be collected from subjects at the time of disease progression, and the BH3 profile of these samples will be compared to subjects' baseline. By measuring the cytochrome c loss in response to other BH3 peptides, such as BAD, MS-1 and HRK, it will be possible to determine whether dependencies on anti-apoptotic proteins other than BCL-2 predicts

CONFIDENTIAL

This document is confidential. Do not disclose or use except as authorized.

resistance to therapy. We can also determine whether BCL-2 dependency predicts response to therapy or risk of tumor lysis syndrome.

We will simultaneously perform dynamic BH3 profiling, in which CLL cells will be treated with duvelisib *ex-vivo*, prior to traditional BH3 profiling. This will also allow us to see the change in mitochondrial priming as well as changes in anti-apoptotic dependencies following treatment with duvelisib.

All peripheral blood samples will promptly be delivered to the laboratory of [name], where they will undergo Ficoll purification and then be viably frozen in FBS with 10% DMSO. The viably-frozen samples will be batched and later transported to the laboratory of [name], where the BH3 profiling assays will be performed.

## 9.2 Cytometry by Time of Flight (CyTOF):

We will obtain samples prior to therapy, after one week of duvelisib monotherapy (cycle 1, day 8) and after three and six months of combination therapy. We will plan to use a panel of monoclonal antibodies targeting 35 markers, including 26 surface membrane and 9 intracellular markers. The Wilcoxon matched-pairs signed rank test will be used to compare percentages of T-cell subsets, NK cells, and monocytes obtained from CyTOF at various time points. As duvelisib is known alter the tumor-promoting effects of T-cell and myeloid cells in the microenvironment, we aim to characterize these changes and correlate our findings with both response to therapy (ORR), complete response (CR) rate as well as toxicity. In particular we will assess how changes in the ratio of regulatory to conventional T cells correlates with immune-mediated toxicities, as has been observed with other PI3K inhibitors.

## 9.3 Minimal Residual Disease (MRD):

All participants will be assessed for minimal residual disease (MRD) on both blood and bone marrow throughout the course of the study. Such patients who have fewer than 0.01% ( $10^{-4}$ ) CLL cell percentage of leukocytes in the bone marrow, as assessed by four-color flow cytometry will be considered to be MRD negative.

CONFIDENTIAL

This document is confidential. Do not disclose or use except as authorized.

### 9.3.1 Adaptive Sequencing Studies

Depending on sample and funding availability, additional testing may also be performed at Adaptive Biotechnologies in Seattle, WA for MRD testing by their NGS platform known as ClonoSEQ. Peripheral blood and/or bone marrow samples will be collected, processed and stored at Dana-Farber Cancer Institute for possible future analysis at Adaptive. Using Adaptive's ClonoSEQ platform, rearranged immunoreceptor loci from genomic DNA will be extracted, amplified, and sequenced using V and J segment primers for each immunoreceptor gene. Tumor-specific clonotypes will be identified for each patient based on their high prevalence in peripheral blood or bone marrow. Sequences will be analyzed using standardized algorithms for clonotype determination. Adaptive MRD levels will be quantified using spiked-in reference sequences.

Adaptive Biotechnologies  
[name]  
Seattle, WA 098102

### 9.3.2 Mayo Clinic Minimal Residual Disease/ Flow Cytometry

Bone marrow and blood samples will be collected for minimal residual disease analysis by Mayo Clinic Genetics by flow cytometry as part of standard of care required disease monitoring per the study calendar in [section 10, and also in Table 9](#).

### 9.5 Pharmacokinetic (PK) Testing (Phase I) :

In the phase I study, PK testing for duvelisib will be performed at baseline, 0.5, 1, 2, 4, 6, 8, 10, , and 24 hours following the initial dose of duvelisib on Day 1. PK testing will be performed at baseline, 0.5, 1, 2, 4, 6, 8, 10, and 24 hours following the initial venetoclax dosing on Day 8 to analyze both duvelisib and venetoclax PK. The 10-hour post dose PK is strongly encouraged, but optional. PK analysis for both drugs will be performed at pre-dose, 1 and 4 hours in subsequent weeks to assess steady-state levels prior to cycle 2 at each venetoclax dose escalation.

	Cycle 1 Day 1 (duvelisib)	Cycle 1 Day 8 (duvelisib + venetoclax)	Cycle 1 On days of venetoclax dose escalation
Pre-dose (-2 hrs)	X	X	X
0.5h post dose (± 5 mins)	X	X	
1h post dose (± 5 mins)	X	X	X
2h post dose (± 5 mins)	X	X	
4h post dose (± 15 mins)	X	X	X
6h post dose (± 15 mins)	X	X	
8h post dose (± 15 mins)	X	X	
10h post dose (± 15 mins) (optional)	X	X	
24h post dose (± 15 mins)	X	X	

CONFIDENTIAL

This document is confidential. Do not disclose or use except as authorized.

Blood will be collected in vacutainers (4.0 ml BD Vacutainer® K2 EDTA Purple Top) at above mentioned time points and centrifuged (within 30 minutes) at a standard speed and time in a refrigerated centrifuge to process the plasma. The processed plasma will be divided and transferred into two cryotubes (primary and secondary; 2X1.8 mL white cryotubes) using transfer pipette. The cryotubes will be stored at -80°C freezer until shipment to bioanalytical laboratory.

Duvelisib and Venetoclax PK analyses will be performed at:

inVentiv Health  
[name],  
Quebec, Quebec, G1P 0A2  
CANADA

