### **5.1.2 Venetoclax:**

Venetoclax will be administered daily, with 28 consecutive days defined as a treatment cycle (up to 42 days for cycle 1) until the time of disease progression without clinical benefit, death, unacceptable toxicity, withdrawal of consent, or physician/patient discussion of discontinuation based on objective disease response, or they elect to go on a new CLL or Richter's directed therapy. The first dose of venetoclax will be given on day 8 of cycle 1 at a starting dose of 10 mg. All patients will be admitted for administration of the initial dose of venetoclax at each dose escalation. Patients will be started on allopurinol and IV hydration for TLS prophylaxis. TLS laboratories will be checked approximately 4, 8, 12, and 24 hours post venetoclax dose. Pre-dose laboratory values will be used as baseline to assess for potential electrolyte abnormalities following venetoclax. Patients can be discharged if no evidence of laboratory TLS 24 hours after dosing, according to the Cairo-Bishop criteria for TLS. If laboratory or clinical TLS is seen, as defined by Cairo-Bishop criteria, patients will be managed as per appendix C. Patients will be admitted weekly for each dose escalation (10 mg, 20 mg, 50 mg, 100 mg, 200 mg, 400 mg) for up to six weeks (42 days) depending on the target dose level. The same rules and TLS laboratory evaluations will be applied for each dose escalation, with the potential to escalate to 100 mg (dose level +1), 200 mg (dose level +2), and 400 mg (dose level +3).

CONFIDENTIAL

This document is confidential. Do not disclose or use except as authorized.

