### **Inpatient:**

When venetoclax dosing is performed as an inpatient, TLS labs must be performed STAT at least at the following time points: pre-dose (within 4 hours before venetoclax administration), and approximately 4, 8, 12, and 24 hours after the first dose of venetoclax and each subsequent dose escalation. Pre-dose laboratory values will be collected and used as baseline to assess potential electrolyte abnormalities occurring post venetoclax administration.

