**Table 9: Study Calendar:**

Cycle = 28 days (except for cycle 1 which will vary in length)	Screening**	Cycle 1 (+3 Days)					Cycle 2 (+7 Days)				Cycles 3-6 (+7 Days)	Cycles 7+ ( 2 cycles +/- 7d until C13, then q3 cycles +/-14d through cycle 60, then q6 months +/- 14 days	End of Treatment 	Active Follow Up (q3 months +/- 14 days ) and Disease Monitoring 	Survival Status	
		Day 1 	Day 2	Day 8 	Day 15 	Day 22 Day 29 Day 36 Day 43	Day 1	Day 8	Day 15	Day 22						Day 1
Procedure / Days	-28-0	Day 1 	Day 2	Day 8 	Day 15 	Day 22 Day 29 Day 36 Day 43	Day 1	Day 8	Day 15	Day 22	Day 1	Day 1				
Informed consent	X															
Duvelisib		X	X	X	X	X	X	X	X	X	X	X (through cycle 12)				
Venetoclax				X	X	X	X	X	X	X	X	X				
Survival Status																X
PK assessments (phase I study only)		X	X	X	X	X										
History and Physical Exam + Vital signs 	X	X		X	X	X	X	X	X	X	X	X	X	X	X	
Serum pregnancy test	X*															
Physical Exam Lymph node measurements		X 		X 												
Quality of life survey (appendix F)		X		X												
Concurrent Medications	X	X		X	X	X	X	X	X	X	X	X	X	X		
Urinalysis	X															
BM aspirate/biopsy 	X 										X	X	X	X		
SPEP + Immunoglobulins 	X										X	X				

CONFIDENTIAL

This document is confidential. Do not disclose or use except as authorized.

Cycle = 28 days (except for cycle 1 which will vary in length)	Screening**	Cycle 1 (+3 Days)					Cycle 2 (+7 Days)				Cycles 3-6 (+7 Days)	Cycles 7+ ( 2 cycles +/- 7d until C13, then q3 cycles +/-14d through cycle 60, then q6 months +/- 14 days	End of Treatment 	Active Follow Up (q3 months +/- 14 days ) and Disease Monitoring 	Survival Status
		Day 1 	Day 2	Day 8 	Day 15 	Day 22 Day 29 Day 36 Day 43	Day 1	Day 8	Day 15	Day 22					
Procedure / Days	-28-0	Day 1 	Day 2	Day 8 	Day 15 	Day 22 Day 29 Day 36 Day 43	Day 1	Day 8	Day 15	Day 22	Day 1	Day 1			
ECOG performance status	X						X				X	X	X	X	
EKG	X 														
Serology: SARS CoV2-,HIV, HCV, HBV 	X														
CT or PET/CT scan and Response Assessment 	X										X	X	X	X	
Hematology (CBC with differential and platelets)	X	X		X	X	X	X	X	X	X	X	X	X	X	

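### Venetoclax samples on escalation days do not measure steady state at the dose being escalated to, and 400 mg has no steady-state sample at all

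*Combined protocol and SAP*

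**What the plan says.** Section 9.5 plans full profiles to 24 h for duvelisib on Day 1 and for both drugs on Day 8, the day of the first venetoclax dose. For later weeks it says that "PK analysis for both drugs will be performed at pre-dose, 1 and 4 hours in subsequent weeks to assess steady-state levels", with the timing given as "prior to cycle 2 at each venetoclax dose escalation". The reduced column of its table is headed "Cycle 1 On days of venetoclax dose escalation" and marks pre-dose, 1 h and 4 h only.

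The PK row of Table 9 (section 10) is limited to phase I. It has marks in the cycle 1 columns and none from cycle 2 onward.

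Section 5.1.2 starts venetoclax at 10 mg on Day 8 and raises it weekly through 20, 50, 100, 200 and 400 mg, as far as the cohort dose requires.

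Section 8.2.1 gives the venetoclax kinetics: "Venetoclax plasma concentrations peaked at approximately 5 to 8 hours after dosing", and "Mean harmonic terminal phase half-life from 17 to 41 hours". For contrast, section 8.1.1 gives duvelisib a peak at about 0.5 to 2 h and a half-life of 7 h.

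Section 13.3 makes PK the phase I secondary endpoint, with non-compartmental parameters summarized descriptively.

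**The concern.** A sample supports a steady-state statement about a dose only if the patient has taken that dose long enough. On an escalation day the patient has taken the old dose for a week and the new dose either not yet (pre-dose sample) or once (1 h and 4 h samples). The last PK day for each patient is therefore the first day on the assigned cohort dose. The post-dose times also end before venetoclax is expected to peak.

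Section 2.5 justifies the low starting dose by a possible CYP3A4 interaction, and section 7.4.1.3 reports that duvelisib raised exposure to a sensitive CYP3A substrate about 4-fold. Venetoclax exposure alongside duvelisib is what this PK work should show. The dose that matters most is 400 mg, the target of the phase II ramp-up in section 5. If first-day values at a new dose were reported as steady-state values, they would understate exposure at that dose.

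**Working it through.** The protocol gives no PK sample size or precision figure, so there is none to reproduce. The check has two parts: a day count that needs no model, and an estimate of size that does.

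**1. Day count.** First day at a ramp step = 8 + 7 × (step − 1), with 10 mg as step 1. The last column assumes that cycle 1 ends about a week after the cohort dose is reached. Sections 5.1.1 (cycle 1 of up to 49 days) and 5.1.2 (ramp-up length tied to the target dose) support this.

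| Cohort dose | First day on it = last PK day | That day's pre-dose value is the trough of | After 7 days on it (about C2D1) |
|---|---|---|---|
| 50 mg | Day 22 | 20 mg | Day 29 |
| 100 mg | Day 29 | 50 mg | Day 36 |
| 200 mg | Day 36 | 100 mg | Day 43 |
| 400 mg | Day 43 | 200 mg | Day 50 |

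No PK sample is scheduled on the days in the last column. A 50, 100 or 200 mg trough exists only from patients who go on to the next dose. No patient goes above 400 mg, so 400 mg has none.

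**2. Peak.** The last post-dose sample is at 4 h and the stated peak is at 5 to 8 h, so sampling ends 1 to 4 h before it.

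**3. Is the pre-dose value a steady-state trough of the preceding dose?** Fraction of steady state after seven days, starting from zero, is 1 − 2^(−168/t½):
- t½ = 17 h: 0.999
- t½ = 41 h: 0.942

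Patients start from the previous ramp dose, not from zero. Superposition in a one-compartment oral model, with absorption set to give a peak at 5 or 8 h, puts the 50, 100 and 200 mg pre-dose values at 96 to 99.9% of their own steady-state troughs. They are valid for those doses. Against the trough at the new, doubled dose they are 48 to 50%.

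**4. First-day exposure at the new dose.** Accumulation ratio R = 1/(1 − 2^(−24/t½)):
- t½ = 17 h: R = 1.60
- t½ = 41 h: R = 3.00

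After a doubling, first-day AUC as a fraction of the new steady-state AUC is (1 + 1/R)/2:
- R = 1.60: (1 + 0.624)/2 = 0.81
- R = 3.00: (1 + 0.334)/2 = 0.67

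For the 20 to 50 mg step it is 0.4 + 0.6/R = 0.77 and 0.60. These formulas treat absorption as fast.

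The AUC fraction measures the size of the gap. It is not something the plan would report, because samples at 0, 1 and 4 h cannot give a 24 h AUC. For the concentrations actually drawn, the same one-compartment model gives, for the steps to 100, 200 and 400 mg, a 1 h value at 56 to 70% and a 4 h value at 63 to 80% of the steady-state value at the same time.

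**5. Duvelisib.** With a 7 h half-life it is at steady state by Day 8, and the 1 h sample lies inside its peak window. The steady-state aim is met for that drug.

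**The case against.** The strongest reply is that section 9.5 does not promise steady state at the cohort dose. It covers both drugs and refers to each escalation. Read that way, the pre-dose samples deliver a venetoclax trough at each completed ramp step, and duvelisib is well served. This stands, and it rules out the broader inference that the schedule yields no steady-state information.

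A reader might also infer that exposure at the MTD goes unobserved whatever the MTD turns out to be. The documents do not support that: for 50, 100 or 200 mg, patients from the next level up supply the trough. The gap is complete only at 400 mg.

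Even there, section 8.2.1 reports roughly dose-proportional steady-state exposure from 150 to 800 mg, so doubling the 200 mg trough gives an estimate for 400 mg. That is usable, but it is extrapolation, and the section does not say that proportionality holds with duvelisib.

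Table 9 leaves some room for doubt. It merges Days 22, 29, 36 and 43 into one column with a PK mark. Section 5 adds three patients at the MTD who start at 20 mg; if the MTD is 400 mg they reach it on Day 36, so a Day 43 sample would follow a week at 400 mg. The section 9.5 table excludes that day because nothing is escalated on it, and it would fall at about C2D1, where Table 9 has no PK mark. For patients who reach 400 mg on Day 43, no reading gives a later sample.

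Finally, neither the MTD rule (section 13.1) nor the phase II response rule (section 13.2) uses PK, and section 13.3 does not say that first-day values will be labeled steady state. Both points are correct and limit the consequence to a secondary, descriptive endpoint.

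**Conclusion.** The point holds for venetoclax only. The escalation-day samples give near-steady-state troughs of the preceding dose and first-day values, cut off before the peak, at the new one. No patient is sampled at steady state on the assigned cohort dose, no steady-state peak or AUC is obtained at any dose, and 400 mg has no steady-state sample under the section 9.5 table.

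These statements rest on the weekly ramp-up and the sampling table alone. The size rests on linear kinetics and the stated 17 to 41 h half-life: first-day exposure after a doubling is about 67 to 81% of the new steady state, an understatement of 19 to 33% if it were presented as steady state. The documents give no half-life with duvelisib; if duvelisib slows clearance, the gap is larger.

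The plan should be corrected, but dose finding and the phase II decision are unaffected.

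**What to change.** **If phase I sampling is still open**, amend section 9.5 and Table 9 as follows:
- Add a pre-dose PK tube at C2D1. Blood is already drawn there (Tables 9 and 10), before study drug, after about seven days at the cohort dose. Under the model above this trough is 97 to 99.9% of steady state for the 100, 200 and 400 mg cohorts.
- Add a venetoclax PK tube to the 8 h tumor lysis draw that phase I inpatients already have at each escalation (sections 5.1.2 and 5.4.1). This reaches the stated peak window on the first day at each dose. It does not give a steady-state peak, and none should be claimed from it.

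The cost is one tube at C2D1 and one per escalation day after Day 8 (five for a patient going from 10 to 400 mg), with their assays and no new visit.

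**If sampling is closed**, as the synopsis and section 5 suggest by describing phase I tumor lysis experience in the past tense, the change is to analysis and wording only:
- Analyze each escalation-day pre-dose venetoclax value as the trough of the preceding dose.
- Do not report the 1 h and 4 h venetoclax values as steady state.
- Confirm from the sample records that no Day 43 sample was taken in patients who started at 20 mg. Then state that steady-state venetoclax exposure at 400 mg with duvelisib was not measured, and that any figure extrapolated from 200 mg assumes dose proportionality holds with duvelisib.
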